4. SUMMARY OF PROPOSAL

PURPOSE:

This study aimed to assess the efficacy of cryotherapy in controlling Peripheral Neuropathy in pediatric tumor patients

BACKGROUND:

Peripheral neuropathy is a serious condition characterized by symmetrical, distal damage to the peripheral nerves that may be caused by several classes of drugs, including chemotherapeutic agents. Chemotherapy-induced peripheral neuropathy (CIPN) is an adverse effect estimated to occur in up to 40% of patients undergoing chemotherapy, with its incidence increasing in patients being treated with multiple agents. Pharmacists play a pivotal role in the prevention and management of CIPN by recommending evidence-based pharmacologic and non-pharmacologic strategies appropriate for the individual patient. Peripheral neuropathy (PN) is a systemic disease characterized by symmetrical, distal damage to the peripheral nerves that negatively impacts patient quality of life (QOL). Prolonged symptoms associated with PN can cause pain, interfere with functional ability (e.g., dressing, driving, house-work), and disrupt emotional health.

HYPOTHESES:

H0 there is no significant difference of cryotherapy in controlling Peripheral Neuropathy in pediatric tumor patients

H1 there is a significant difference of cryotherapy in controlling Peripheral Neuropathy in pediatric tumor patients

RESEARCH QUESTION:

Is there a significant difference of cryotherapy in controlling Peripheral Neuropathy in pediatric tumor patients?

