5. CONDUCT OF PROJECT

Please give a description of the research methodology that will be used

- Nerve conduction studies (NCS) and somatosensory-evoked potentials (SSEPs) were used to assess peripheral neuropathy pre and post intervention.
-

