6. PARTICIPANTS AS THE SUBJECTS OF THE RESEARCH

Describe the number of participants and important characteristics (such as age, gender, intellectual ability etc.). Specify any inclusion/exclusion criteria to be used.

Subjects:

Eighty children with tumors were enrolled in this study and were assessed for eligibility. Their aged ranged from six and fourteen years. They were assigned randomly into two equal groups. Group (A) study group received the same medical care and shockwave, three times / weak for three successful months. And group (B) control group received medical care and standard chemotherapy only. Nerve conduction studies (NCS) and somatosensory-evoked potentials (SSEPs) were used to assess peripheral neuropathy pre and post intervention. All children were assisted before and after three months of intervention.

Inclusion criteria:

1. Their age will ranging from six to fourteen years.
2. Children participated in this study will from both sexes.
3. Children receiving chemotherapy as primary treatment, postoperative surgical removal of tumors or with conjunction with radiotherapy
4. All children have polyneuropathy caused by chemotherapy.

Exclusion criteria:

1. Children with Epilepsy.
2. Children with blood clotting disorder.
3. Children have Open wounds / broken skin
4. Children with severe cardiac disease
5. Uncooperative patients.

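### The hypothesis concerns cryotherapy but group A is given shockwave, and neither NCS nor SSEPs is designated primary, so the trial as described cannot decide its stated H0

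*Protocol*

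**What the plan says.** **Purpose and hypotheses (Protocol section 4).** The purpose reads "This study aimed to assess the efficacy of cryotherapy in controlling Peripheral Neuropathy in pediatric tumor patients". The null hypothesis is "H0 there is no significant difference of cryotherapy in controlling Peripheral Neuropathy in pediatric tumor patients", H1 is its mirror image, and the research question asks "Is there a significant difference of cryotherapy in controlling Peripheral Neuropathy in pediatric tumor patients". All four name cryotherapy. None names a measured parameter, a comparator group or a time point.

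**Outcomes (section 5, repeated in section 6).** "Nerve conduction studies (NCS) and somatosensory-evoked potentials (SSEPs) were used to assess peripheral neuropathy pre and post intervention". Neither modality is called primary, and no nerve or parameter is given.

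**Design (section 6).** "They were assigned randomly into two equal groups". The study arm is described as "Group (A) study group received the same medical care and shockwave", and the comparator as "group (B) control group received medical care and standard chemotherapy only". On timing: "All children were assisted before and after three months of intervention".

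**The concern.** A hypothesis is decided by a comparison on an outcome. Here both links are weak.

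The first break is the intervention. If group A receives what section 6 describes, a difference between A and B is evidence about that intervention and not about the one in H0. No choice of outcome or analysis repairs this.

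The second is the outcome. With two unranked modalities, and a hypothesis worded broadly enough to fit either, a reader of the protocol cannot tell which result was meant to decide the trial. If the deciding parameter is chosen after the results are seen, the nominal significance level no longer describes the risk of a false claim.

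**Working it through.** **1. The intervention, side by side.**

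| Place in the protocol | Intervention named |
|---|---|
| Section 4, purpose, H0, H1, research question | Cryotherapy |
| Section 10, significance | Cryotherapy |
| Section 6, group A | Shockwave |

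The text at hand does not say that the two are the same or that group A receives both. The randomised contrast in section 6 is shockwave plus medical care against group B. H0 concerns cryotherapy. The contrast therefore does not test H0 as worded.

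**2. The outcome.** Sections 5 and 6 give two modalities, no ranking and no parameter. H0 speaks only of controlling neuropathy. Nothing in the protocol selects one result as decisive.

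**3. What can be inferred.** Section 6 gives random allocation, a labelled control group and a single post-baseline assessment at three months. The intended contrast (A versus B) and time point follow from these.

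**4. The protocol's own figure.** Section 6 gives 80 children in two equal groups, so 80 / 2 = 40 per group at most. The 80 cannot be re-derived, because the text gives no alpha, power, effect size, SD or dropout. Forty analysed per group is a best case for two reasons. Section 6 says the eighty were assessed for eligibility without saying that all passed, and section 8 removes withdrawn children's data from the analysis.

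**5. Illustration of the outcome gap.** Assumptions, none from the protocol: one A-versus-B test per modality, two-sided 0.05 each, no true effect, and a significant result on either one counts.

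- Independent tests: 1 − (1 − 0.05)² = 1 − 0.9025 = 0.0975.
- Correlated tests: 1 − P(|Z₁| ≤ 1.96 and |Z₂| ≤ 1.96), with (Z₁, Z₂) bivariate normal with correlation r. This gives 0.0907 (r = 0.5), 0.0835 (r = 0.7) and 0.0704 (r = 0.9).
- Simulated t-tests with 40 per group, 40,000 trials for each r, give 0.098, 0.092, 0.083 and 0.072 for r = 0, 0.5, 0.7 and 0.9, in agreement.
- If each modality yields several parameters, the count is higher. For four independent parameters, 1 − 0.95⁴ = 0.185; for six, 1 − 0.95⁶ = 0.265. These counts are assumed.
- Under the opposite rule, where both modalities must be significant, the chance is at most 0.05 (0.05² = 0.0025 if independent).

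**6. What joint primaries would cost.** Splitting alpha to 0.025 each holds the false-positive chance at 0.0494 (r = 0) to 0.0362 (r = 0.9). With the best-case 40 per group and an assumed 80% power, the normal approximation to the detectable difference is (z₁₋α/₂ + z₀.₈) × √(2/40):

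- alpha 0.05: (1.960 + 0.842) × 0.2236 = 0.626 SD
- alpha 0.025: (2.241 + 0.842) × 0.2236 = 0.689 SD

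The noncentral t gives slightly larger values, 0.634 and 0.701 SD. At 0.634 SD, power per modality falls from 0.800 to 0.708.

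**The case against.** The strongest reply has four parts.

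- **The design is already there.** Section 6 names a study group, a control group, randomisation and a three-month assessment. A reader might infer from the bare H0 that the trial has no defined comparison or time point. The protocol does not support that. This part of the objection stands, and what remains is a minor wording point. Likewise, the pre/post wording leaves a within-group reading open, but no section proposes within-group tests as evidence of efficacy.
- **Some of the detail may sit in a statistical analysis plan.** Alpha, the multiplicity rule and the analysis model are commonly fixed there, and their absence here is not a fault. This stands too. It does not cover the intervention mismatch, which is a contradiction inside the protocol. Nor does it fully cover the missing primary outcome, because a protocol that states a hypothesis should say what decides it.
- **The error-rate figures rest on an assumed rule.** A reader might infer that this trial's false-positive rate is close to 10%. The protocol does not say that either modality suffices, and it is equally silent on requiring both, which would keep the rate at or below 5%. The figures show what the ambiguity permits, not a property of the trial.
- **The intervention conflict is a separate defect.** It is, and it is the more serious of the two. It belongs here because a hypothesis cannot be tied to the A-versus-B comparison until the two sections agree on what group A receives.

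**Conclusion.** The point holds in two parts of unequal weight.

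The main part needs no assumption: section 4 and section 6 name different interventions, so the randomised comparison does not test the stated H0. The documents do not show which section is in error, and this review takes no position on it.

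The second part is that no outcome is designated to decide the trial. Its size cannot be fixed from the protocol. Under the assumed either-counts rule with two tests at two-sided 0.05, the false-positive chance is about 7% to 10% (correlation 0.9 to 0), against 5% for one named test. Under a both-required rule there is no inflation. The detectable-difference figures apply only if all 80 children are randomised and analysed.

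**What to change.** 1. **Reconcile sections 4 and 6** so that the purpose, H0, H1 and research question name what group A actually receives. Naming a primary outcome does not substitute for this.
2. **Before outcome data are examined, name one primary parameter**, an NCS or an SSEP measure chosen by the investigators. State H0 as no difference between groups A and B in that parameter at three months. Either a baseline-adjusted comparison or a between-group test of change would do. Make all other parameters secondary. Stating the contrast this way also closes the within-group reading.
3. **If both modalities must be primary**, split the alpha and accept the loss of power shown in the working.
4. **If outcome data have already been examined**, report the choice of primary as post hoc. The protocol leaves this open: section 6 describes enrolment in the past tense, section 7 describes recruitment in the future tense.

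**Cost.** With outcome data unexamined, naming the primary and restating H0 is a change of wording: no extra children, visits or measurements, since baseline and three-month assessments are already planned. The downside is that a positive result on another parameter can no longer be the main finding, and a poorly chosen primary may miss an effect that appears elsewhere.

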5. CONDUCT OF PROJECT

Please give a description of the research methodology that will be used

- Nerve conduction studies (NCS) and somatosensory-evoked potentials (SSEPs) were used to assess peripheral neuropathy pre and post intervention.
-

6. PARTICIPANTS AS THE SUBJECTS OF THE RESEARCH

Describe the number of participants and important characteristics (such as age, gender, intellectual ability etc.). Specify any inclusion/exclusion criteria to be used.

Subjects:

Eighty children with tumors were enrolled in this study and were assessed for eligibility. Their aged ranged from six and fourteen years. They were assigned randomly into two equal groups. Group (A) study group received the same medical care and shockwave, three times / weak for three successful months. And group (B) control group received medical care and standard chemotherapy only. Nerve conduction studies (NCS) and somatosensory-evoked potentials (SSEPs) were used to assess peripheral neuropathy pre and post intervention. All children were assisted before and after three months of intervention.

Inclusion criteria:

1. Their age will ranging from six to fourteen years.
2. Children participated in this study will from both sexes.
3. Children receiving chemotherapy as primary treatment, postoperative surgical removal of tumors or with conjunction with radiotherapy
4. All children have polyneuropathy caused by chemotherapy.

Exclusion criteria:

1. Children with Epilepsy.
2. Children with blood clotting disorder.
3. Children have Open wounds / broken skin
4. Children with severe cardiac disease
5. Uncooperative patients.

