10. SIGNIFICANCE/BENEFITS

Outline the potential significance and/or benefits of the research

The use of freezing temperatures for analgesia has been recorded for thousands of years. Modern cryotherapy has slowly become a well-established treatment option for peripheral neuralgias and neuropathic pain conditions. Cryoneurolysis induces peripheral nerve damage and causes nerves to undergo axonotmesis followed by Wallerian degeneration. Nerve regrowth occurs but may not lead to permanent pain relief. The therapy continues to be optimized and is best used for well-defined small nerves that are easy to target. The use of cryotherapy has been indicated for intercostal neuralgia, occipital neuralgia, trigeminal neuralgia, phantom limb pain, obturator neuralgia, genitofemoral neuralgia, and intractable perineal pain.

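### Group A is described as receiving shockwave, but the purpose, hypotheses and rationale concern cryotherapy, so the trial as written does not test its own hypothesis

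*Protocol*

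**What the plan says.** Section 4 of the protocol (Summary of Proposal) states the purpose: "This study aimed to assess the efficacy of cryotherapy in controlling Peripheral Neuropathy in pediatric tumor patients". The null hypothesis reads "H0 there is no significant difference of cryotherapy in controlling Peripheral Neuropathy in pediatric tumor patients", the alternative "H1 there is a significant difference of cryotherapy in controlling Peripheral Neuropathy in pediatric tumor patients", and the research question asks "Is there a significant difference of cryotherapy in controlling Peripheral Neuropathy in pediatric tumor patients". Section 10 (Significance/Benefits) bases its rationale on the same treatment: "Modern cryotherapy has slowly become a well-established treatment option for peripheral neuralgias and neuropathic pain conditions".

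Section 6 (Participants as the Subjects of the Research) is the only place that says what each arm receives. For the study arm: "Group (A) study group received the same medical care and shockwave, three times / weak for three successful months". For the control arm: "And group (B) control group received medical care and standard chemotherapy only".

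Section 5 (Conduct of Project) lists the nerve conduction and evoked potential assessments and no treatment. Section 11 (Risks) names neither intervention.

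**The concern.** Cryotherapy and shockwave are different physical interventions. The purpose, hypotheses and rationale are about the first, and the treatment description is about the second. One of the two must be wrong.

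- **If section 6 is followed**, the null hypothesis about cryotherapy is never tested. Any difference in nerve conduction or evoked potentials between the groups would be credited to a treatment that no child received.
- **If section 4 is followed**, the only treatment description is wrong. The only stated schedule belongs to shockwave, so staff would have no frequency, duration or method for cryotherapy.

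Consent and safety are also affected. Section 8 undertakes to tell parents about the purpose, the procedures and the possible benefits. On the present text, the purpose and benefits would describe one treatment and the procedure another. Section 10 says that one form of the cold treatment, cryoneurolysis, damages peripheral nerves, and section 6 admits only children who already have polyneuropathy from chemotherapy. Which treatment they get therefore bears on their risk, and the exclusion criteria cannot be judged until it is known.

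**Working it through.** No calculation decides this point. The check is to set every mention of the intervention side by side.

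| Place in the protocol | Intervention named |
|---|---|
| Section 4, purpose | Cryotherapy |
| Section 4, H0 | Cryotherapy |
| Section 4, H1 | Cryotherapy |
| Section 4, research question | Cryotherapy |
| Section 5, methodology | None (assessments only) |
| Section 6, group A | Shockwave |
| Section 6, group B | Neither |
| Section 6, exclusion criteria | Neither |
| Section 8, consent and withdrawal | Neither |
| Section 10, rationale | Cryotherapy and cryoneurolysis |
| Section 11, risks | Neither |

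Step 1. The randomised contrast is defined by section 6 alone. Read literally, it compares medical care plus shockwave with medical care and standard chemotherapy. Cryotherapy is in neither arm.

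Step 2. The hypotheses concern an effect of cryotherapy. A contrast without cryotherapy in either arm does not estimate that effect.

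Step 3. Size. Section 6 gives eighty children in two equal groups, so 80 / 2 = 40 in group A. The number of these stated to receive cryotherapy is 0, that is 0 / 40 = 0%. The result would be 0% for any other group size, so a larger trial would not help.

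Step 4. Could something else explain the mismatch? The group A sentence is complete, with a treatment, a frequency and a duration. It is current text, and no redaction or broken table is involved. Some pages of the protocol are not available for review. They might name the intervention, but they could not make sections 4 and 10 agree with section 6.

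Step 5. Could it be left to a statistical analysis plan? No. Such a plan can define how arms are compared, but it cannot choose which treatment the study arm receives.

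**The case against.** The strongest reply is that this is a drafting slip. Shockwave appears once, while four statements in section 4 and the whole of section 10 point to cryotherapy. If group A is in fact given cryotherapy, the comparison does address H0, and only one word is wrong. That reading is plausible, but the protocol does not confirm it. Even if it is right, the protocol then has no correct description of its study arm, so an amendment is needed either way.

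Three narrower points deserve weight.

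- The sections on risks, exclusions and consent name neither treatment. Their silence contradicts nothing, and the conflict lies between sections 4 and 10 on one side and section 6 on the other.
- The figure of 40 is inferred. Section 6 says "Eighty children with tumors were enrolled in this study and were assessed for eligibility", which leaves some doubt about how many were randomised. The share stated to receive cryotherapy is zero whatever the number.
- Section 6 is written in the past tense. If children have already been treated, correcting the wording may not be enough. Rewriting the hypotheses to match a treatment already given would be a change after the fact and would have to be reported as such.

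These points affect how the correction is made. They do not remove the contradiction.

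**Conclusion.** The concern holds and must be fixed before the protocol can be relied on. As written, none of the children in group A (0 of 40, assuming all eighty are randomised equally) is stated to receive the intervention named in H0 and H1, so the comparison of group A with group B carries no information on cryotherapy. This is a judgement on the text and makes no claim about what was actually delivered. It rests on section 6 being the only description of the arms in the available document.

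**What to change.** The sponsor should decide which intervention is meant and name that one in the purpose, both hypotheses, the research question, the group A description and the rationale. The exclusion criteria, the risks and the parent information should be made to match it.

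- **If cryotherapy is meant**, replace shockwave in section 6 and state the modality, body site, temperature, session length and schedule. Confirm whether the frequency and duration now attached to shockwave apply. Make clear whether surface cooling or cryoneurolysis is intended, since section 10 covers both terms and inserting the word cryotherapy would leave this open.
- **If shockwave is meant**, rewrite the purpose, hypotheses, research question and rationale around it.

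In both cases, add a sentence limiting conclusions to the intervention actually delivered to group A. If treatment has started, confirm from treatment records what was given before amending, and date and disclose the change.

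The cost is a wording amendment and matching parent information, with no extra patients or procedures. That assumes the error is one of wording. If the treatment already given differs from the one intended, the cost is higher and the document does not allow it to be estimated.

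### Does naming chemotherapy only for the control group mean that the arms differ in chemotherapy as well as in the study intervention?

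*Protocol*

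**What the plan says.** The arms are defined in section 6 of the protocol, under Subjects. The study arm: "Group (A) study group received the same medical care and shockwave, three times / weak for three successful months". The control arm, in the next sentence: "And group (B) control group received medical care and standard chemotherapy only". Chemotherapy is named in the second sentence and not in the first.

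The same section sets eligibility for all participants. Inclusion criterion 3 is "Children receiving chemotherapy as primary treatment, postoperative surgical removal of tumors or with conjunction with radiotherapy", and criterion 4 is "All children have polyneuropathy caused by chemotherapy". On allocation it says "They were assigned randomly into two equal groups", with 80 children in all. The outcomes are nerve conduction studies and somatosensory-evoked potentials, taken before and after three months. Section 5 repeats the outcome measures and adds nothing about background treatment.

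**The concern.** In the control-arm sentence, chemotherapy is joined to medical care by *and*, as if the two were separate components. The study arm shares the first component by name, but not the second. Taken literally, group A is medical care plus shockwave and group B is medical care plus chemotherapy. That is two differences between two arms, and no analysis could separate them.

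This would matter because chemotherapy is the protocol's own stated cause of the condition. Section 4 says "Chemotherapy-induced peripheral neuropathy (CIPN) is an adverse effect estimated to occur in up to 40% of patients undergoing chemotherapy". If one arm had less neurotoxic exposure during the three months, its nerve conduction could look better at the end whether or not the intervention worked. Randomisation would not help: it balances what children bring to the trial, not a treatment difference written into the arms.

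**Working it through.** The protocol gives no figure to reproduce on this point, so the check is mainly a comparison of texts, all from section 6.

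| Element | Group A (study) | Group B (control) |
|---|---|---|
| Medical care | yes, *the same* | yes |
| Chemotherapy named in the arm sentence | no | yes |
| Added physical intervention | yes | no (*only*) |
| Criterion 3: receiving chemotherapy | applies | applies |
| Criterion 4: polyneuropathy caused by chemotherapy | applies | applies |
| Any statement that chemotherapy is stopped or withheld | none | none |

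1. *Same* needs something to refer to. The only other care described is group B's, and that description includes chemotherapy. *Only* in the control sentence marks B as the arm without the addition. Together the two words describe an add-on design.
2. Criterion 3 is in the present tense and is not limited to one arm. A child allocated to A is therefore a child receiving chemotherapy. For the literal reading to hold, chemotherapy would have to end on allocation to A, and the protocol says nothing of the kind.
3. Criterion 4 fixes the cause of the neuropathy at entry as chemotherapy for every child. The arms cannot differ in cause. The most that could differ is continuing exposure over the three months.

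The scale can be shown with assumed inputs. Let δ be the shift in the outcome, in SD units, produced by three months of chemotherapy compared with none. Let p_A and p_B be the shares of children in each arm who receive it. Then

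bias in favour of A = δ × (p_B − p_A).

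The protocol gives no δ. Taking 0.3 to 0.6 SD purely as an assumption:

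- Literal reading (p_B = 1, p_A = 0): bias = 0.3 to 0.6 SD.
- Section read as a whole (p_A = p_B): bias = δ × 0 = 0, whatever δ is.

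For comparison, 80 / 2 = 40 per arm, and the standard error of a difference in means is √(2/40) = 0.224 SD. With an assumed two-sided 5% level and 80% power, neither of which the protocol states, the smallest detectable effect is about 0.634 SD from the t distribution. Under the literal reading and no intervention effect, the test statistic would centre on 0.3/0.224 = 1.34 to 0.6/0.224 = 2.68. A two-sample t-test would then be significant about 26% to 75% of the time instead of 5%. These figures apply only if group A receives no chemotherapy at all, which criterion 3 contradicts.

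**The case for a change.** The strongest counter-argument is that arm definitions belong in the protocol and cannot be left to an analysis plan, and that these two do not match. *The same* comes before group B has been described and, even read forward, attaches to medical care and not to chemotherapy. Criterion 3 describes children at entry and does not say what each arm receives afterwards. A reader who wants a sentence confirming equal chemotherapy over three months will not find one. Correcting the wording and tabulating exposure by arm would cost very little.

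Some of this stands. The asymmetry is real, the arm sentences sit awkwardly beside criterion 3, and concurrent chemotherapy in group A has to be inferred. The inference is strong, however. The literal reading needs an event the protocol never mentions, and it empties both *same* and *only* of meaning. The paragraph also contains other language slips, such as the spelling of *week* in the study-arm sentence, so loose drafting is the likelier explanation. A table of agents and exposure by arm is sensible description, but it is the kind of item commonly left to an analysis plan, which is not shown here. That a correction is cheap does not make it consequential.

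**Conclusion.** No change to the plan follows. The arm sentences are not parallel, and this is a clerical slip. Read with the eligibility criteria, the random allocation and the words *same* and *only*, section 6 describes two groups of 40 children who share background treatment that includes chemotherapy, with the added physical intervention as the one planned difference. The planned difference in chemotherapy is zero. Chance differences in exposure between arms are balanced in expectation by randomisation, apart from any effect of the intervention itself on how chemotherapy is given. The 0.3 to 0.6 SD shift has no basis in the protocol and should not be read as an estimate of bias. Parallel wording would leave treatment, outcomes, analysis and conclusions as they are.

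This rests on one assumption: that criterion 3 describes treatment continuing in both arms, as its present tense and lack of any arm restriction imply. If records showed that chemotherapy was given by design to one arm only, the concern would return in full. Nothing here is a view on which cancer treatment is right. The mismatch between cryotherapy in the stated aim (section 4) and shockwave in the arm description (section 6) is a separate question and is not settled here.
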